### 6.7.1. Use of specified study materials

When materials are provided by GSK Biologicals, it is MANDATORY that all clinical samples (including serum samples) be collected and stored exclusively using those materials in the appropriate manner. The use of other materials could result in the exclusion of the subject from the Per-Protocol analysis (See Section [11.5](#) for the definition of cohorts to be analyzed). The investigator must ensure that his/her personnel and the laboratory(ies) under his/her supervision comply with this requirement. However, when GSK Biologicals does not provide material for collecting and storing clinical samples, appropriate materials from the investigator's site must be used. Refer to the Module on Clinical Trial Supplies in the SPM.

## 6.7.2. Biological samples

**Table 8 Biological samples**

Sample type	Sample type	Quantity	Timepoint	Study groups
Whole blood	Blood sampling for HIV, HCV and HBsAg	~17 mL	Screening #1	P-Fx NP-Fx
			Screening #2	Infectivity control
	Blood sampling for assessment of parasitemia (blood smear and PCR)	~4 mL	Visit 4 (Day 27) Visit 5 (Day 28) Visit 6 (Day 29) Visit 7 (Day 30) Visit 8 (Day 31) Visit 9 (Day 32) Visit 10 (Day 33) Visit 11 (Day 34) Visit 12 (Day 35) Visit 13 (Day 36) Visit 14 (Day 37) Visit 15 (Day 38) Visit 16 (Day 39) Visit 17 (Day 40) Visit 18 (Day 42) Visit 19 (Day 44) Visit 20 (Day 46) Visit 21 (Day 48) Visit 22 (Day 50)	All subjects
			Screening #1 Visit 1 (Day 1)** Visit 3 (Day 22) Visit 22 (Day 50) Visit 23 (Day 190)	
	Blood sampling for PBMC and plasma repository	~40 mL	Screening #1 Visit 1 (Day 1)** Visit 2 (Day 8) Visit 3 (Day 22) Visit 22 (Day 50) Visit 23 (Day 190)	P-Fx NP-Fx
			Screening #1 Visit 1 (Day 1) Visit 2 (Day 8)	
			Screening #2 Visit 3 (Day 22) Visit 22 (Day 50) Visit Par*	
			Visit 22 (Day 50)	
			Visit Par*	
	Blood sampling for hematology and biochemistry analysis	~7.5 mL	Screening #1 Visit 1 (Day 1) Visit 2 (Day 8)	P-Fx NP-Fx
			Screening #2 Visit 3 (Day 22)	Infectivity control
			Visit 22 (Day 50)	All subjects
			Visit Par*	

\*Biochemistry and hematology parameters will be collected the day of first parasitemia (between Visit 4 [Day 27] and Visit 21 [Day 48]).

\*\*Blood sample might not be drawn at Visit 1 if this visit occurs less than one week after the screening visit, at the discretion of the investigator

### 6.7.3. Laboratory assays

Please refer to [APPENDIX A](#) for a detailed description of the assays performed in the study. Please refer to [APPENDIX B](#) for the address of the clinical laboratories used for sample analysis.

Serological assays for the determination of anti-CS antibodies will be performed by enzyme-linked immunosorbent assay (ELISA) at laboratories designated by GSK Biologicals using standardized and validated procedures.

Serological assays for the determination of anti-HBs antibodies will be performed by chemiluminescence enzyme immunoassay (CLIA) at GSK Biologicals' laboratory using standardized and validated procedures.

**Table 9 Assays for humoral immunity (antibody determination)**

System	Component	Method	Kit/Manufacturer	Unit	Cut-off	Laboratory
Serum	Plasmodium falciparum.Circumsporozoite Protein.R32LR Ab.IgG	ELISA	In house	EU/mL	1.9	CEVAC
Serum	Plasmodium falciparum.Circumsporozoide Protein.R32LR Ab.IgG Avidity	ELISA	In house	%	Not applicable	CEVAC
Serum	Plasmodium falciparum.anti-C-Term Circumsporozoide Ab.IgG	ELISA	In house	EPT	100	WRAIR
Serum	Plasmodium falciparum.anti-C-Term Circumsporozoide Ab.IgG avidity	ELISA	In house	Avidity Index	Not applicable	WRAIR
Serum	Plasmodium falciparum.Circumsporozoite Full length(N+C-Terminal) Recombinant+NANP Protein+NVPD Protein Ab.IgG	ELISA	In house	1/DIL	Not applicable	WRAIR
Serum	Plasmodium falciparum.anti-full length Circumsporozoide Ab.IgG avidity	ELISA	In house	Avidity Index	Not applicable	WRAIR
Serum	Hepatitis B Virus.Surface Ab (Total Ig)	CLIA	ADVIA Centaur anti-HBs2 (Siemens Healthcare)	mIU/mL	6.2	GSK Biologicals*

**Ab** = antibody; **Ig** = immunoglobulin; **ELISA** = enzyme-linked immunosorbent assay; **CEVAC** = Center For Vaccinology; **EPT** = endpoint titer; **WRAIR** = Walter Reed Army Institute of Research; **CLIA** = chemiluminescence enzyme immunoassay

\*GSK Biologicals laboratory refers to Clinical Laboratory Sciences (CLS) In Rixensart, Belgium; Wavre, Belgium.

Other assays on stored serum, PBMCs and plasma samples may be performed to investigate the safety and/or vaccine induced anti-malaria and hepatitis B immune responses.

The repository laboratory for serum samples will be GSK Biologicals' clinical laboratories and for plasma and PBMC samples will be Precision Bioservices, Inc.

Assessment of *P. falciparum* parasitemia will be performed by blood slide microscopy reading and real-time PCR at WRAIR, as applicable.

**Table 10 Assessment of *P. falciparum* parasitemia**

System	Component	Method	Unit	Laboratory
Whole blood	Plasmodium falciparum parasites*	Blood slide microscopy reading	Parasite/ $\mu$ L	WRAIR
Whole blood	Plasmodium falciparum parasites*	Real-time PCR	Positive/negative	WRAIR

**WRAIR** = Walter Reed Army Institute of Research; **PCR** = polymerase chain reaction

\**P. falciparum* parasite count includes blood-stage parasites.

Hematology, biochemistry and screening tests (e.g., HIV, leukocytes) will be performed by different methods/assays at Quest Diagnostics, Inc., (all except pregnancy testing) and at the WRAIR (pregnancy testing).

**Table 11 Hematology, biochemistry and screening tests**

System	Component	Method	Scale	Laboratory
Serum	HIV-IgG + Ag (SER,GLR)	Immunoassay	Qualitative	Quest Diagnostics, Inc.
Serum	Hepatitis B Virus.Surface Ab	CLIA	Qualitative	Quest Diagnostics, Inc.
Serum	Hepatitis C virus Ab	Immunoassay	Qualitative	Quest Diagnostics, Inc.
Urine	$\beta$ -HCG*	Immunoassay	Qualitative	WRAIR
Whole blood	Hemoglobin Leukocytes (White Blood Cells) Platelets	Not applicable	Quantitative	Quest Diagnostics, Inc.
Serum	Alanine Aminotransferase Aspartate Aminotransferase Creatinine	Not applicable	Quantitative	Quest Diagnostics, Inc.

**HIV** = human immunodeficiency virus; **IgG** = immunoglobulin G; **Ag** = antigen; **Ab** = antibody; **CLIA** = chemiluminescence enzyme immunoassay; **HCV** = hepatitis C virus;  **$\beta$ -HCG** = beta-human chorionic gonadotropin; **WRAIR** = Walter Reed Army Institute of Research

\*Urinary pregnancy test

Additional exploratory testing on the vaccine and/or on the disease under study may be performed within the framework of the study if deemed necessary for accurate interpretation of the data or should such assay(s) become available at GSK. These assays may not be represented in the objectives/endpoints of the study protocol.

The GSK Biologicals' clinical laboratories have established a Quality System supported by procedures. The activities of GSK Biologicals' clinical laboratories are audited regularly for quality assessment by an internal (sponsor-dependent) but laboratory-independent Quality Department.

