**LIST OF ABBREVIATIONS**

AE:	Adverse Event
ALT:	Alanine Aminotransferase
AS01E:	GSK's proprietary Adjuvant System containing MPL, QS-21 (25 µg MPL and 25 µg QS-21) and liposome
AST:	Aspartate Aminotransferase
β-HCG:	Beta-Human Chorionic Gonadotropin
CHMI:	Controlled Human Malaria Infection
CI:	Confidence Interval
CLIA:	Chemiluminescence Enzyme Immunoassay
CS:	Circumsporozoite protein of Plasmodium falciparum
eCRF:	electronic Case Report Form
ELISA:	Enzyme-Linked Immunosorbent Assay
EoS:	End of Study
ES:	Exposed Set
eTDF:	Electronic Temperature excursion Decision Form
FDA:	Food and Drug Administration, United States of America
Fx:	Fractional
GCP:	Good Clinical Practice
GSK:	GlaxoSmithKline
GMC:	Geometric Mean Concentration
HBsAg:	Hepatitis B surface antigen
HCV:	Hepatitis C Virus
HIV:	Human Immunodeficiency Virus
ICF:	Informed Consent Form
ICH:	International Conference on Harmonization

IEC:	Independent Ethics Committee
IgG:	Immunoglobulin G
IMP:	Investigational Medicinal Product
IRB:	Institutional Review Board
MedDRA:	Medical Dictionary for Regulatory Activities
MPL:	3-O-desacyl-4'-monophosphoryl lipid A (produced by GSK)
NHANES I:	National Health And Nutrition Examination Survey I
P. falciparum:	Plasmodium falciparum
PBMC:	Peripheral blood mononuclear cells
PCD:	Primary Completion Date
PCR:	Polymerase Chain Reaction
pIMD:	Potential Immune-Mediated Disease
PPS:	Per-Protocol Set
QS-21:	Quillaja saponaria Molina, fraction 21 (Licensed by GSK from Antigenics Inc., a wholly owned subsidiary of Agenus Inc., a Delaware, USA corporation)
RCC:	Reverse Cumulative Curve
SAE:	Serious Adverse Event
SBIR:	Randomization System on Internet
SD:	Standard Deviation
SDV:	Source Document Verification
SPM:	Study Procedures Manual
VE:	Vaccine Efficacy
WBC:	White Blood Cell
WRAIR:	Walter Reed Army Institute of Research

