**Table 3** **Blinding of study epochs**

Study Epochs	Blinding
Epoch 001	Open
Epoch 002	Open
Epoch 003	Open
Epoch 004	Open

- **Sampling schedule:**

For subjects from the P-Fx and NP-Fx groups:

- Blood samples for assessment of anti-CS and anti-HBs immune response and for serum repository will be collected at screening, Day 1\*, on the day of challenge (Day 22), 28 days post-challenge (Day 50) and at study end (Day 190).
- Blood samples for peripheral blood mononuclear cells (PBMCs) and plasma repository will be collected at screening, Day 1\*, 7 days post-booster (Day 8), on the day of challenge (Day 22), 28 days post-challenge (Day 50) and at study end (Day 190).

\*Before vaccine administration. These samples might not be drawn if Visit 1 occurs less than one week after screening, at the discretion of the investigator.

For all subjects:

- Blood samples for the evaluation of biochemistry (alanine aminotransferase [ALT], aspartate aminotransferase [AST], creatinine) and hematology (hemoglobin, leukocytes [white blood cells; WBC], platelets) parameters will be collected at screening, Day 1\*, 7 days post-booster\* (Day 8), Day 22, the day of first parasitemia and 28 days post-challenge (Day 50). Following a bleeding procedure failure or laboratory failure, repeat bleeds can be considered upon investigator discretion no more than three times, or if medically indicated for full investigation of a potential adverse event or clarification of subject eligibility.

\*Not applicable for the infectivity controls.

- Blood sample for assessment of parasitemia (blood smear and PCR) will be collected daily for 14 days (from Day 27 [Visit 4] to Day 40 [Visit 17]) and then every two days for nine days (Day 42 [Visit 18], Day 44 [Visit 19], Day 46 [Visit 20], Day 48 [Visit 21] and Day 50 [Visit 22]). Exceptionally this can occur within 1 or 3 days if the subject cannot make the visit or for schedule conflicts. For subjects who develop malaria, blood smear and PCR may be discontinued once the subject has three consecutive negative smears (separated by more than 12 hours) following the initial treatment.

- Blood samples for testing of HIV, hepatitis C virus (HCV) and HBsAg will be collected from all subjects at screening.
- Urinary pregnancy test (urine beta-human chorionic gonadotropin [ $\beta$ -HCG]) will be performed on all women at screening, at Day 1\* and on the day of challenge (Day 22).

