### 5.3. Exclusion criteria for enrollment

Deviations from exclusion criteria are not allowed because they can potentially jeopardize the scientific integrity, regulatory acceptability of the study or subject safety. Therefore, adherence to the criteria as specified in the protocol is essential.

The following criteria should be checked at the time of study entry. If ANY exclusion criterion applies, the subject must not be included in the study:

For all subjects except the infectivity control subjects:

- Any medical condition that in the judgment of the investigator would make intramuscular injection unsafe.
- History of any reaction or hypersensitivity likely to be exacerbated by any component of the vaccine.
- History of anaphylaxis post-vaccination.

For all subjects:

- Use of any investigational or non-registered product (drug or vaccine) other than the study vaccine during the period starting 30 days before Day 1 (Day -29 to Day 1) (for P-Fx and NP-Fx groups)/before the malaria challenge (for infectivity control subjects), or planned use during the study period.
- Chronic administration (defined as more than 14 days in total) of immunosuppressants or other immune-modifying drugs during the period starting six months prior to Day 1 (for P-Fx and NP-Fx groups) or malaria challenge (for infectivity control subjects). For corticosteroids, this will mean prednisone  $\geq 20$  mg/day, or equivalent. Inhaled and topical steroids are allowed.
- Administration of long-acting immune-modifying drugs at any time during the study period (e.g. infliximab).
- Chronic use of antibiotics with anti-malarial effects (e.g., tetracyclines for dermatologic patients, sulfa for recurrent urinary tract infections, etc.).
- Planned administration/administration of a vaccine not foreseen by the study protocol in the period within seven days of Day 1 (for P-Fx and NP-Fx groups) or the malaria challenge (for infectivity control subjects).
- Concurrently participating in another clinical study, at any time during the study period, in which the subject has been or will be exposed to an investigational or a non-investigational vaccine/product (pharmaceutical product or device).
- Seropositive for HIV, HBsAg or HCV.
- Planned travel to malaria endemic areas during the study period.
- Any confirmed or suspected immunosuppressive or immunodeficient condition, based on medical history and physical examination.

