### 6.7.4.2. Hematology/Blood chemistry

**Table 13 Hematology/biochemistry read-outs**

Blood sampling timepoint		Study groups	Number of subjects	Component
Type of contact and timepoint	Sampling timepoint			
Screening #1	SCR#1	P-Fx NP-Fx	~40**	HIV IgG + Ag HBsAg Ab HCV Ab Hemoglobin Leukocytes (WBC) Platelets
Screening #2	SCR#2			ALT AST Creatinine
Visit 1 (Day 1) Visit 2 (Day 8)	Vaccination day Post-vaccination			Hemoglobin Leukocytes (WBC) Platelets
Visit 3 (Day 22) Visit 22 (Day 50) Visit Par*	Post-challenge Post-challenge	All subjects	~64	ALT AST Creatinine

**HIV** = human immunodeficiency virus; **IgG** = immunoglobulin G; **Ag** = antigen; **HBsAg** = hepatitis B surface antigen; **Ab** = antibody; **HCV** = hepatitis C virus; **WBC** = white blood cell; **ALT** = alanine aminotransferase; **AST** = aspartate aminotransferase

\*Biochemistry and hematology parameters will be collected the day of first parasitemia (between Visit 4 [Day 27] and Visit 21 [Day 48]).

\*\*A minimum of 20 subjects per group (P-Fx and NP-Fx) is anticipated

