**6.7.5. Immunological correlates of protection**

No correlate of protection has been demonstrated so far for the CS antigen.

For the HBsAg, the conventional correlate of protection is anti-HBs antibody concentrations above 10 mIU/mL [[European Consensus Group on Hepatitis B Immunity, 2000](#)].

The investigator is encouraged to share the immunological assay results for non-responders with the study subjects.

For the subjects identified as non-responders, it remains the responsibility of the investigator in charge of the subject's clinical management to determine the medical need for re-vaccination and to re-vaccinate the subjects as per local/regional practices.

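### Protocol Tables 11 and 13 list hepatitis B surface antibody as the screening test, while the exclusion criterion and procedure text name surface antigen

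*Protocol*

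**What the plan says.** **The criterion.** Protocol Section 5.3 lists, for all subjects, "Seropositive for HIV, HBsAg or HCV" among the exclusion criteria, and adds: "If ANY exclusion criterion applies, the subject must not be included in the study". The list of abbreviations gives HBsAg as "Hepatitis B surface antigen".

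**The procedure text.** The sampling schedule in Section 3, like the synopsis, says: "Blood samples for testing of HIV, hepatitis C virus (HCV) and HBsAg will be collected from all subjects at screening". The procedure tables (Tables 4 and 5, with footnote b to each), the eligibility check in Section 6.6.3, the sampling description in Section 6.6.15 and Table 8 all name HBsAg as well.

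**The assay tables.** Table 11 gives the hepatitis B screening component as "Hepatitis B Virus.Surface Ab", a qualitative chemiluminescence immunoassay at the external screening laboratory. Table 13 lists the virology components at screening as "HIV IgG + Ag HBsAg Ab HCV Ab". Neither table contains a surface-antigen test.

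**The antibody elsewhere.** Anti-HBs is a secondary immunogenicity endpoint, measured from screening onward (Section 11.2). Section 6.7.5 treats it as a marker of protection: "For the HBsAg, the conventional correlate of protection is anti-HBs antibody concentrations above 10 mIU/mL".

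**The concern.** The two tables that name the screening analyte point to a different analyte from the one on which eligibility depends. Surface antigen and antibody to it are different measurements with different meanings, and here the difference matters more than usual. The P-Fx and NP-Fx subjects have all been vaccinated with RTS,S in MALARIA-092. The protocol expects that vaccine to induce hepatitis B antibody and follows the antibody as a wanted response. A positive antibody result is therefore unremarkable in these subjects and says nothing about whether the antigen is present.

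If the laboratory order were built from Tables 11 and 13, the test would not deliver the information that Section 5.3 needs before vaccination and challenge. The word seropositive adds to the risk, because it reads naturally with an antibody result. Section 6.7 also points to the investigator's undertaking to run only assays described in the protocol, so the assay tables need to be right.

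**Working it through.** No arithmetic applies, and the plan states no figure on this point. The check is a comparison of every place in the protocol that names the hepatitis B screening test.

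| Place in protocol | Role | Analyte named |
|---|---|---|
| Section 5.3 | Exclusion criterion | HBsAg |
| Synopsis and Section 3, sampling schedule | What is sampled at screening | HBsAg |
| Section 5.1, recruitment plan | Results that controls may carry over | HBsAg |
| Tables 4 and 5, with footnote b | Procedures and results to check | HBsAg |
| Section 6.6.3 | Eligibility check | HBsAg |
| Section 6.6.15 and Table 8 | Purpose of the 17 mL sample | HBsAg |
| Table 11 | Screening assay specification | Surface antibody |
| Table 13 | Screening read-outs | Surface antibody |

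1. **Could Ab be loose shorthand for the antigen test?** No. The legends of both tables define Ag as antigen and Ab as antibody, separately. The HIV entry uses the two kinds of marker side by side: "HIV IgG + Ag HBsAg Ab HCV Ab Hemoglobin Leukocytes (WBC) Platelets".

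2. **Do the labels mean antibody elsewhere?** Yes. Table 9 uses almost the same component name for the quantitative anti-HBs assay (total immunoglobulin, cut-off 6.2 mIU/mL, sponsor's laboratory). Table 12 uses the Table 13 label for the immunogenicity read-out at priority rank 5. One label therefore serves both a wanted vaccine response and an exclusion screen.

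3. **Is an antibody test needed at screening for another reason?** Yes, but it is already provided for. Section 11.2 includes screening among the anti-HBs endpoint timepoints, and Tables 9 and 12 cover that measurement. The qualitative row in Table 11 is a separate test that sits with HIV and HCV, so it belongs to eligibility screening.

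4. **Does the SAP settle it?** No. It specifies no screening assay.

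5. **Does the inconsistency reach the efficacy analysis?** No. The primary endpoint is blood-slide parasitemia compared by Fisher's exact test, and the power table in Section 11.4 uses only infection proportions and group sizes. None of these depends on the hepatitis B test.

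**The case against.** The strongest reply is that this is a labelling slip in two tables. The criterion and the text that governs conduct consistently name HBsAg, and the sample is drawn to establish HBsAg status. The natural reading is that the antigen test is run and the component name in Tables 11 and 13 is wrong. Nothing in the protocol says that the laboratory order is taken from these two tables. Operational detail sits in the Study Procedures Manual, and the order form is not available. For controls, Section 5.1 lets HBsAg results be carried over from a separate generic screening protocol. Most of this stands. It makes a wrong component name the likeliest cause and leaves actual harm conditional on how the order was written. It does not remove the inconsistency, because Tables 11 and 13 are the only tables that specify the screening analyte.

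Two stronger readings are tempting, and the documents do not support either.

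- **That the vaccine groups would be emptied, or selected toward anti-HBs non-responders.** An antibody result does not meet a criterion stated in terms of antigen, and the protocol itself treats anti-HBs as protective, so staff would have to misread an expected vaccine response. Nor can a count be given. No anti-HBs positivity rate at screening is stated, and the number screened is uncertain. Section 11.4 gives about 100 challenged vaccinees, so 100 × 0.8 = 80 after refusals, or 80 × 0.8 = 64 if the drop-out rate is also taken before screening.
- **That the trial has no antigen test.** The procedure tables and Table 8 call for HBsAg. What is missing is an entry for it in the two assay tables.

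**Conclusion.** The point holds as an internal inconsistency that is wrong as written: the test listed in Tables 11 and 13 measures a different analyte from the one in Section 5.3 and the procedure text. Its extent is two tables against the rest of the protocol, for a screen that applies to all subjects. No number of affected subjects can be derived.

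The conclusion that the listed test cannot apply the criterion follows directly from the tables' own definitions. The expectation that vaccinees carry anti-HBs rests on the protocol's account of the vaccine and its endpoints, not on a stated rate. Any practical consequence assumes that the laboratory order follows the two tables, which the documents do not show. The correction should be made because it concerns an eligibility and safety screen and costs very little.

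**What to change.** - Reconcile Tables 11 and 13 with Sections 3, 5.3, 6.6.3 and 6.6.15, so that the hepatitis B screening entry names the analyte that the exclusion criterion already uses.
- Keep anti-HBs only as the immunogenicity read-out in Tables 9 and 12.
- Clarify in Section 5.3 what seropositive means for HBsAg, so that antibody status is not read as meeting the criterion.
- Check the laboratory order and the Study Procedures Manual against the corrected tables.

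The cost is a correction to two tables, one clarified phrase and a check of the order. The sample of about 17 mL for HIV, HCV and HBsAg is already planned, so no further blood draw is needed. The analysis plan does not change.

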## 6.7.4. Biological samples evaluation

### 6.7.4.1. Immunological read-outs

**Table 12 Immunological read-outs**

Blood sampling timepoint		Study groups	Number of subjects	Component	Components priority rank
Type of contact and timepoint	Sampling timepoint				
Screening #1	Screening	P-Fx NP-Fx	~40*	Anti-CS Ab	1
Visit 1 (Day 1)	Vaccination day			Anti-CS avidity index	2
Visit 3 (Day 22)	Challenge day			Anti-C term Ab	3
Visit 22 (Day 50)	Post-challenge			Anti-C term avidity index	4
Visit 23 (Day 190)	Post-challenge			HBsAg Ab	5

**CS** = circumsporozoite; **Ab** = antibody; **HBsAg** = hepatitis B surface antigen

\*A minimum of 20 subjects per group (P-Fx and NP-Fx) is anticipated

In case of insufficient blood sample volume to perform assays for all antibodies, the samples will be analyzed according to priority ranking provided in [Table 12](#).

Additional serological assays for the determination of anti-full length CS antibodies titers and avidity will be performed by ELISA at WRAIR following the same order as in the table above (i.e., determination of antibody titers before avidity).

